5.4 Packaging and Administration of Study Device

The device comes ready packaged and sterile for use. Each unit is a 2.5-3.5 gram ingot that can be molded as needed by the surgeon and applied to the cut site of the sternum. The control comes similarly packaged. Each dosage of either the study device or the control should be individually separated and numbered. Individual envelopes with printouts of the corresponding numbers will be used for randomization.

5.5 Receiving, Storage, Dispensing and Return

5.5.1 Receipt of Device Supplies

Upon receipt of the of the study treatment supplies, an inventory must be performed and a device receipt log filled out and signed by the person accepting the shipment. It is important that the designated study staff counts and verifies that the shipment contains all the items noted in the shipment inventory. Any damaged or unusable study device in a given shipment (study device or comparator) will

CONFIDENTIAL

This material is the property of the Loma Linda University Medical Center. Do not disclose or use except as authorized in writing by the study sponsor

be documented in the study files. The investigator must notify study sponsor of any damaged or unusable study treatments that were supplied to the investigator's site.

5.5.2 Storage

The device and the control will be stored in a locked file cabinet with the OR Coordinator.

5.5.3 Dispensing of Study Device

Once randomization has occurred the study investigators will be notified of the study patient's treatment allocation and the printout kept with the study patient's source documents. The study patient's charts will be labeled in order for them to easily be recognized as a study patient. The morning of the planned surgery, the Nurse Manager in the operating room will be notified that the patient is a study patient and that they will receive BoneSeal or Ostene during the surgery. The study investigator will obtain the product prior to the start of surgery. The study device will be kept with the OR Coordinator in a locked file cabinet in order for the study device to remain separate and in a temperature controlled environment. Regular study device reconciliation will be performed to document treatment assigned, treatment consumed, and treatment remaining. This reconciliation will be logged on the device reconciliation form, and signed and dated by the Principal Investigator.

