12.1	FUNDING SOURCE	19
12.2	CONFLICT OF INTEREST	19
12.3	DISCLOSURE	20
12.4	SUBJECT STIPENDS OR PAYMENTS.....	20
13	PUBLICATION PLAN	20
14	REFERENCES.....	20
15	ATTACHMENTS	21

CONFIDENTIAL

This material is the property of the Loma Linda University Medical Center. Do not disclose or use except as authorized in writing by the study sponsor

List of Abbreviations

CRF	Case Report Form
FDA	Food and Device Administration
GCP	Good Clinical Practice
IRB	Institutional Review Board
HA	Hydroxyapatite
PLA	Poly-lactic acid
PEG	Polyethylene glycol
CABG	Coronary Artery Bypass Grafting
OR	Operating Room

CONFIDENTIAL

This material is the property of the Loma Linda University Medical Center. Do not disclose or use except as authorized in writing by the study sponsor

Study Summary

Title	Effectiveness of BoneSeal® on sternal bone hemostats in patients undergoing cardiothoracic surgery
Short Title	Effectiveness of BoneSeal®
Protocol Number	Not yet assigned
Methodology	Prospective, randomized, open-label, study design
Study Duration	Estimated duration for the main protocol (start of screening November 2016) to (last subject processed and finishing the study November 2017)
Study Center(s)	Single-center
Objectives	To evaluate the effectiveness of BoneSeal® on bone hemostats in patients undergoing cardiothoracic surgery.
Number of Subjects	60
Diagnosis and Main Inclusion Criteria	Adult patients over 18 years undergoing coronary artery bypass grafting with or without valve replacement or repair ultimately requiring a sternotomy.
Study Product, Dose, Route, Regimen	BoneSeal® Bone Wax Hemostats Dosage regimen is as follows: 1 to 2 units (2.5 or 3.5 grams) per surgery as determined by the surgeon.
Reference therapy	Ostene®
Statistical Methodology	Statistical methods for evaluating postoperative bleeding and need for blood transfusions will include a Fisher's exact test (2 groups, 2 outcomes).

CONFIDENTIAL

This material is the property of the Loma Linda University Medical Center. Do not disclose or use except as authorized in writing by the study sponsor

1 Introduction

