5.3 Method for Assigning Subjects to Treatment Groups

Subjects will be randomized on the day of surgery. A number will be assigned to each package – study device and control. This number will be printed on a page and a page sealed that is then sealed in an envelope. On the day of surgery, an envelope will be pulled and opened by the OR Coordinator and confirmed by the investigator. The corresponding number will be selected from the labeled packages. The printed number will be labeled with the subject's information filed as a source document. The number and corresponding assignment (study device or control) will be noted in the patient's record.

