6.4 Schedule of Events

Pre-Operative	Study Data Point 1 – Intra-Operative Hemostasis Evaluation	Study Data Points 2 – Post-Operative 24 hours	Study Data Point 3 – Post-Operative 30 Day Follow-up by phone
Inclusion/Exclusion	Notation of severity of osteoporosis	Hemoglobin Levels	Survival Documentation
Informed Consent	Qualitative evaluation osteoporosis during surgery	Notation of post- operative blood product usage	Notation of any visits for infection or complications.
Hemoglobin levels	Qualitative evaluation of bleeding of the cut sternum during the surgery	6 hours Post-op Surgical Site Drainage	
	Qualitative evaluating of the ease of use of the product	12 hours Post-op Surgical Site Drainage	
	Notation of in- operative blood product usage	18 hours Post-op Surgical Site Drainage	
	Notation of a re-bleed occurrence	24 hours Post-op Surgical Site Drainage	

7 Statistical Plan

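### The arm is disclosed before the sternum is opened and written in the patient's record, so pre-application grades and post-operative transfusion decisions are exposed to it without need

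*Combined protocol and SAP*

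**What the plan says.** The Study Summary declares the design: "Prospective, randomized, open-label, study design". Section 5.3 sets the timing: "On the day of surgery, an envelope will be pulled and opened by the OR Coordinator and confirmed by the investigator". It also says what is written down: "The number and corresponding assignment (study device or control) will be noted in the patient's record".

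Section 5.5.3 tells the investigators the arm: "Once randomization has occurred the study investigators will be notified of the study patient's treatment allocation". It then places the handover of the product ahead of the operation: "The study investigator will obtain the product prior to the start of surgery".

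The Schedule of Events (6.4) lists these items in the intra-operative column: "Notation of severity of osteoporosis", a second qualitative evaluation of osteoporosis, and "Qualitative evaluation of bleeding of the cut sternum during the surgery". Section 3.2 makes the surgeon's grade of bleeding and hemostatic action during application primary endpoint 1. Chest tube output is primary endpoint 4, intra- and post-operative transfusion quantities are endpoint 5, and infection or complications to day 30 are endpoint 6.

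The plan describes no masked assessor, no limit on who may read the assignment, no transfusion criterion, and no grading before the envelope is opened.

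**The concern.** Two kinds of information do not depend on the product and could be collected without knowledge of the arm.

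The first is the state of the bone and its bleeding before anything is applied. A surgeon who already knows the arm may grade these differently by arm. They are then no longer clean baseline measurements and cannot safely be used to check balance or to adjust. Section 7.1 relies on an ANCOVA to explain any differences found, and adjusting for a covariate graded with knowledge of the arm can create a difference rather than explain one.

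The second is post-operative care. Ordering blood is partly a matter of judgement, and its quantity is a primary endpoint. The day-30 assessment of complications also involves judgement. The arm in the patient's record lets both be influenced. The background in Section 1.1 already expresses an expectation that bleeding may continue under Ostene, so it is reasonable to guard against expectation effects.

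**Working it through.** **Order of events.** The plan's only sample-size figure is 60, which Section 7.1 says was not derived statistically, so there is nothing to reproduce. The main check is to set disclosure against assessment.

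| Item | When | Is the arm known? | Avoidable? |
|---|---|---|---|
| Osteoporosis (6.4) | Intra-operative | Yes | Yes, it does not depend on product |
| Bleeding of cut sternum before application (6.4, if graded then) | Intra-operative, timing not given | Yes | Yes |
| Bleeding and hemostatic action during application (3.2) | With product in hand | Yes | No |
| Re-bleeding, ease of use | After or during application | Yes | No |
| Intra-operative transfusion | During surgery | Yes | No |
| Post-operative transfusion | First 24 hours (6.4) | Can be read in the record | Largely |
| Drainage at 6, 12, 18, 24 hours | Fixed times, measured volume | Can be read in the record | Largely, and less open to bias |
| Day-30 assessment | In person or by phone (6.3) | Can be read in the record | Largely |

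Two steps are inferences. The grading surgeon is taken to be among the notified investigators, or to see the product collected before surgery. Post-operative staff are taken to have access to the record.

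**Illustration 1: an adjusted comparison of drainage.** None of these inputs is in the documents: true osteoporosis grade X = 0, 1, 2; correlation 0.5 with drainage (SD 1); no treatment effect; a fraction f of one arm graded one level too high where a higher level exists.

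- Slope on the true grade: b = 0.5 / SD(X).
- Spurious difference in mean grade: f × P(X < 2).
- Pooled ANCOVA slope: the sum of the two arms' covariances of drainage with the recorded grade, divided by the sum of the two arms' variances of that grade.
- Bias = -(pooled slope) × (spurious difference).

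For equal thirds and f = 0.3:
- SD(X) = 0.816, so b = 0.5/0.816 = 0.612.
- Spurious difference = 0.3 × 2/3 = 0.20.
- Pooled slope = (0.408 + 0.347)/(0.667 + 0.627) = 0.584.
- Bias = -0.584 × 0.20 = -0.117 SD.

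| True grade split | f = 0.3 | f = 0.5 |
|---|---|---|
| 33/33/33% | 0.584 × 0.200 = 0.117 | 0.585 × 0.333 = 0.195 |
| 50/30/20% | 0.587 × 0.240 = 0.141 | 0.582 × 0.400 = 0.233 |
| 25/50/25% | 0.639 × 0.225 = 0.144 | 0.629 × 0.375 = 0.236 |

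The bias favours the over-graded arm. With an assumed 30 per arm, the standard error of the adjusted difference is about √(2/30) × √(1 - 0.25) = 0.22 SD, so the bias is roughly 0.5 to 1.1 standard errors. The range is not a bound: a 60/30/10% split gives 0.17 and 0.28.

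**Illustration 2: transfused or not, by the planned Fisher test.** Assumptions: 30 per arm, true rate 30% or 50% in both arms, and awareness lowering the recorded rate in one arm by d. The rejection probability is the sum of the binomial probabilities over all tables with Fisher p ≤ alpha.

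| d | alpha 0.05 | alpha 0.10 |
|---|---|---|
| 0 | 0.026-0.027 | 0.052-0.056 |
| 5 points | 0.039-0.040 | 0.070-0.078 |
| 10 points | 0.077-0.089 | 0.125-0.150 |

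Both alphas are shown because Section 7.1 raises alpha without giving its value.

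**The case against.** The strongest reply is that the trial is declared open-label and follows its own design, so nothing here contradicts anything. That stands: this is a design weakness, not an inconsistency. It does not answer the point, because open-label use requires the surgeon to know the arm when applying the product. It does not require it when grading bare bone, and it does not require the arm to be in the chart.

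Three stronger readings are tempting, and the documents do not support them.

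- A reader might infer that early opening inflates the false-positive rate for the surgeon's bleeding grade. Section 3.2 ties that primary endpoint to application, when the surgeon holds the product, so later opening cannot mask it. A grade made before application is a baseline and cannot show a treatment effect. Section 7.2 also lists only descriptive statistics for hemostasis scores.
- A reader might infer that early opening produces patients randomized and then found ineligible in the operating room. Section 6.4 checks eligibility pre-operatively, and no exclusion in Section 4.2 depends on what is seen after sternotomy.
- A reader might infer that post-operative staff are told the arm. The documents say only that it is noted in the record. Section 5.5.3 labels charts to identify study patients, and its notice to the Nurse Manager may or may not name the specific product.

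It is also fair to say that osteoporosis is not a named covariate, that the illustrations rest on unsourced inputs, and that waiting for product with an open sternum could itself affect blood loss. The last point shapes the fix.

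**Conclusion.** The point holds in a limited form. The arm is disclosed before osteoporosis and any pre-application bleeding can be graded, and it is recorded where post-operative staff could read it. The plan gives no reason for either, and both can be avoided.

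The size cannot be derived from the plan. If osteoporosis became an ANCOVA covariate under the assumptions shown, the bias would be about 0.12-0.24 SD in favour of the over-graded arm. If awareness moved the recorded transfusion rate by 5-10 points, Fisher's test at 0.05 would reject in about 4-9% of null trials instead of under 3%. Only the post-operative share of that shift could be prevented. Whether any shift would occur is unknown.

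The change is worth making before enrolment, because grades made with knowledge of the arm cannot be repaired in the analysis. It does not make the intra-operative endpoints masked.

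**What to change.** 1. In 5.3 and 5.5.3, have the OR Coordinator open the envelope only after sternotomy, once osteoporosis and a pre-application bleeding grade are written on the CRF. Keep the numbered packages at hand in or next to the operating room so that application is not delayed. Reword the notification of investigators and the collection of product to match.
2. In 3.2 and 6.4, state that the pre-application bleeding grade is a baseline, separate from the endpoint grade made during application. At present 3.2 says during application and 6.4 only during surgery.
3. In 5.3, record only the package number in the chart used by post-operative staff. Hold the assignment in the study source file, with immediate access for safety, until the 24-hour and day-30 data are recorded. Word the notice to the Nurse Manager so that it does not name the arm.
4. If osteoporosis is to be an ANCOVA covariate, name it in Section 7 and define its scale.

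The cost is a few sentences, slightly more operating-room logistics and an unmasking route. The numbered packages and the OR Coordinator's role already exist, so no extra staff, patients or visits are needed. Hemostatic action, bleeding during application, re-bleeding, ease of use and intra-operative transfusion stay open-label. The documents do not say who orders post-operative blood; if it is the operating team, step 3 protects less.

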5.5.4 Return or Destruction of Study Device

At the completion of the study, there will be a final reconciliation of device shipped, device consumed, and device remaining. This reconciliation will be logged on the device reconciliation form, signed and dated. Any discrepancies noted will be investigated, resolved, and documented prior to return or destruction of unused study device. Device destroyed on site will be documented in the study files.

6 Study Procedures

6.1 Study Data Point 1

Hemostasis during surgery will be determined by surgeon's qualitative evaluation. Notation of re-bleed will be made. Re-application of product will not occur.

6.2 Study Data Point 2

Postoperative bleeding will be evaluated by documentation surgical site drainage and the use of blood products.

6.3 Study Data Point 3

30 day post-op follow-up to all for sufficient time to heal and evaluate for possible post-operative infection or complications. This evaluation can be conducted either in person or by phone.

CONFIDENTIAL

This material is the property of the Loma Linda University Medical Center. Do not disclose or use except as authorized in writing by the study sponsor

6.4 Schedule of Events

Pre-Operative	Study Data Point 1 – Intra-Operative Hemostasis Evaluation	Study Data Points 2 – Post-Operative 24 hours	Study Data Point 3 – Post-Operative 30 Day Follow-up by phone
Inclusion/Exclusion	Notation of severity of osteoporosis	Hemoglobin Levels	Survival Documentation
Informed Consent	Qualitative evaluation osteoporosis during surgery	Notation of post- operative blood product usage	Notation of any visits for infection or complications.
Hemoglobin levels	Qualitative evaluation of bleeding of the cut sternum during the surgery	6 hours Post-op Surgical Site Drainage	
	Qualitative evaluating of the ease of use of the product	12 hours Post-op Surgical Site Drainage	
	Notation of in- operative blood product usage	18 hours Post-op Surgical Site Drainage	
	Notation of a re-bleed occurrence	24 hours Post-op Surgical Site Drainage	

7 Statistical Plan

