7.1 Sample Size Determination

The power of 60 patients was not determined statistically. The number was determined at the request of the sponsor based on their minimum requirements. In order to compensate for the lack of statistical sample size determination, an increase in alpha and adding an ANCOVA to explain any differences found will be utilized.

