7.2 Statistical Methods

Descriptive statistics for mean homeostasis scores, the length of operation time, the surgical drainage output, and the ease of BoneSeal® application.

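### The ANCOVA offered in place of a sample size calculation is worded as a follow-up to differences already found; it should be the planned analysis, adjusted for pre-operative hemoglobin

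*Combined protocol and SAP*

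**What the plan says.** Section 7.1 (Sample Size Determination) states "The power of 60 patients was not determined statistically" and "The number was determined at the request of the sponsor based on their minimum requirements". To make up for this it proposes "an increase in alpha and adding an ANCOVA to explain any differences found will be utilized". It gives no value for the raised alpha, and no response variable, covariates or model for the ANCOVA.

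Section 7.2 (Statistical Methods) does not mention the ANCOVA. Its whole content is "Descriptive statistics for mean homeostasis scores, the length of operation time, the surgical drainage output, and the ease of BoneSeal® application". The Study Summary adds a Fisher's exact test on a two-by-two table for bleeding and transfusion, which takes no covariate.

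Section 6.4 (Schedule of Events) lists hemoglobin before surgery and again at 24 hours, and drainage at 6, 12, 18 and 24 hours. The intra-operative column has two osteoporosis entries, "Notation of severity of osteoporosis" and "Qualitative evaluation osteoporosis during surgery", neither with a scale. Osteoporosis appears in no objective, endpoint, randomization step or analysis. Section 3.2 makes post-operative hemoglobin relative to baseline, and chest tube output, primary endpoints 3 and 4.

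**The concern.** The ANCOVA is the only model in the plan, and the plan relies on it to offset an unjustified sample size. Covariate adjustment can do that work only if it is fixed in advance and is itself the between-arm comparison. Worded as an explanation of differences already observed, it comes too late to recover power, and it leaves open which covariates are used and whether the adjusted or the unadjusted result carries the conclusion. That discretion comes on top of an alpha that is to be raised by an unstated amount.

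Meanwhile a covariate well suited to one primary endpoint, pre-operative hemoglobin, is already collected. Osteoporosis severity is collected too, with no stated use.

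**Working it through.** **Inputs.** Total N is 60 (Study Summary; Section 7.1). The allocation ratio is not stated in Section 5.3; 1:1, so 30 per arm, is assumed. Alpha is not stated; two-sided 0.05 is assumed, with 0.10 as an alternative. No SD, effect size or correlation is given, so effects are in SD units and correlations r are assumed over a range. The plan has no power figure to reproduce.

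**1. An ANCOVA run only after a difference is found.** If the adjusted test follows only a significant unadjusted test, trials in which both are significant are a subset of those in which the unadjusted test is. Power cannot rise. Simulation (40,000 replicates, 30 per arm, effect 0.5 SD, alpha 0.05):

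| r | Unadjusted | Both required | Pre-specified ANCOVA |
|---|---|---|---|
| 0.3 | 48.1% | 44.5% | 51.1% |
| 0.5 | 47.6% | 43.4% | 58.6% |

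**2. Free choice between the two results.** With no true effect, reporting whichever p-value is smaller gives a type I error of 0.064, 0.073 and 0.081 at r = 0.3, 0.5 and 0.7, against a nominal 0.05. At a nominal 0.10 it gives 0.124, 0.141 and 0.155. The pre-specified ANCOVA stays at about 0.05 (0.049 to 0.050 at these r).

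**3. Hemoglobin adjusted for its baseline.** Assume equal SD before and after surgery and pre-post correlation r.
- Change-score variance: 2σ²(1 − r).
- ANCOVA variance: σ²(1 − r²).
- Ratio: (1 − r²) / [2(1 − r)] = (1 + r)/2.

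This is 0.65 at r = 0.3, 0.75 at r = 0.5 and 0.85 at r = 0.7. These ratios leave out the degree of freedom spent on the covariate.

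**4. What osteoporosis could add for drainage.** The residual variance factor is 1 − r², and equivalent N is 60/(1 − r²). The detectable difference (80% power, alpha 0.05, t-based) is 0.736 × √(1 − r²) SD. Power is for a 0.6 SD effect.

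| r | Variance factor | Equivalent N | Detectable difference (SD) | Power |
|---|---|---|---|---|
| 0 | 1.00 | 60 | 0.736 | 62.8% |
| 0.2 | 0.96 | 62.5 | 0.721 | 64.5% |
| 0.3 | 0.91 | 65.9 | 0.702 | 66.8% |
| 0.5 | 0.75 | 80 | 0.637 | 75.1% |

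At r = 0.2 or below the gain is negligible. For scale, moving from alpha 0.05 to 0.10 with no adjustment takes power for 0.6 SD to about 74%, close to the best adjusted case shown.

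**5. Timing of the osteoporosis entries.** Under Section 5.3 the envelope is opened on the day of surgery. Under Section 5.5.3 the investigators are told the allocation and fetch the product before surgery starts. Under Section 6.4 both osteoporosis entries are intra-operative. The notation is therefore made by staff who can know the arm, and nothing places it before the product is applied.

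**6. The two osteoporosis rows.** Primary endpoint 1 (Section 3.2) needs a grade of bleeding and a grade of hemostatic action. The intra-operative column is headed as a hemostasis evaluation and has a row for bleeding of the cut sternum, but none that names hemostatic action. The row "Qualitative evaluation osteoporosis during surgery" may be a slip for that grade. The documents do not settle this.

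**The case against.** A reader might infer that osteoporosis enters no analysis and that precision is therefore being lost. The documents do not support that. The unspecified ANCOVA could include it, so the most that can be said is that no analysis names it. Nothing links it to drainage or hemoglobin, and step 4 shows a gain that runs from negligible to useful depending entirely on an assumed correlation.

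A reader might also infer that recording osteoporosis before the envelope is opened is a small matter of timing. It is not. Both entries are intra-operative, so it would mean moving randomization and product retrieval into the operation, or adding a pre-operative assessment that the protocol lacks. Nor is it safe to drop one of the two rows as a duplicate, given step 6.

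On the ANCOVA itself, it can be said that the wording need not mean a conditional test; it may mean adjusting for baseline differences between arms. That is possible, but covariates chosen for imbalances seen in the data are still chosen after the fact. The plan does not say the smaller p-value will be reported, so step 2 shows what the open choice permits and does not predict what will happen.

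The reach is limited. Of the six primary endpoints, ANCOVA naturally suits hemoglobin and drainage. It does not suit the ordinal grades, re-bleeding, infection or the Fisher test. This stands.

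**Conclusion.** The concern holds for the ANCOVA. As worded in Section 7.1 it cannot supply the compensation claimed for it, whatever the correlation. With an assumed r of 0.5 and an effect of 0.5 SD, the gap between a pre-specified ANCOVA and the sequential use is 59% against 43% power. For hemoglobin, baseline adjustment gives 65-85% of the change-score variance for r between 0.3 and 0.7, assuming equal SDs. Any gain for drainage from adjusting for pre-operative hemoglobin depends on a correlation that the documents do not give.

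For osteoporosis the conclusion is narrower: its use is undefined, and as collected it is too exposed to knowledge of the arm to be a main covariate. All figures rest on 30 per arm, no dropout and assumed correlations. This should be corrected before any outcome data are analysed.

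**What to change.** - In Section 7.2, make ANCOVA the planned between-arm analysis of 24-hour hemoglobin and 24-hour drainage, with arm and pre-operative hemoglobin as fixed terms, run whatever the unadjusted result. Remove from Section 7.1 the wording that ties it to differences found.
- State the alpha and whether it is two-sided.
- If osteoporosis is to be used, define its scale and name it only in a pre-specified sensitivity analysis, noting that it is recorded during surgery with allocation known.
- Before changing any row of the Section 6.4 schedule, confirm whether the second osteoporosis row was meant to be the hemostatic-action grade of primary endpoint 1.

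**Cost.** The ANCOVA and alpha changes are text only, since pre-operative hemoglobin is already collected. The analysis takes slightly more work and one or two degrees of freedom. An osteoporosis scale, or a correction to the schedule, would also need a small change to the case report form.
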